12.0 Assessments/Samples/Data Collection

12.1. WP1&2 Submission of Study Data

Consent forms

Where paper consent forms have been completed, a scanned copy of the completed Informed Consent document will be returned to CTRU via the CTRU secure file transfer system (SFT).

Non-registration

Non-registration data will be collected via remote data entry (RDE) on electronic case report forms (eCRFs). Access to the live database will be provided by CTRU to site staff following site authorisation to start recruitment where (i) self-delivered RDE guidance training has been completed and (ii) the member of staff has the relevant delegated duty assigned on the authorised personnel log.

Registration, baseline and follow up data

Registration data is submitted via the CTRU 24-hour system. The baseline eligibility checklist is completed on paper and a scanned copy returned to CTRU via the CTRU SFT, all other baseline data is collected via RDE on eCRFs. Access to the live database will be provided by CTRU to site staff following site authorisation to start recruitment where (i) self-delivered RDE guidance training has been completed and (ii) the member of staff has the relevant delegated duty assigned on the authorised personnel log.

Participant questionnaires

Baseline questionnaires may be administered by the research team in person/on paper or over the telephone/on paper *prior* to registration. Scanned copies of paper questionnaires will be returned to CTRU via the CTRU SFT. Where electronic questionnaire administration of the baseline questionnaire is required, this will be indicated during registration and will be administered by the CTRU after registration. Non-responders to the electronic baseline questionnaire will receive 1 reminder.

Postal and electronic follow up questionnaires will be administered by CTRU using the preference indicated at registration. Telephone follow up questionnaire administration will be completed by the research team and a scanned copy of the paper form returned via CTRU SFT. Non-responders will receive 1 reminder.

Participating sites will be expected to maintain a file of essential study documentation (electronic Investigator Site File), which will be provided by the CTRU, and keep copies of all completed CRFs for the study.

Where central collection of reports is undertaken by the CTRU for central monitoring purposes it is the responsibility of site to obliterate all personal identifiable data prior to sending to the CTRU and use the study number plus date of birth and initials to identify the participant.

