10.5. WP1 Registration

Informed consent for entry into the study must be obtained prior to registration.

Following confirmation of informed consent and eligibility participants will be registered into the study by an authorised member of staff at the study research site. Registration will be performed centrally using the CTRU automated, secure, 24-hour registration system which can be accessed via the web. To register using the web-based system a staff site email address, site code and Personal Identification Number (PIN) will be required. Authorisation codes and PINs will be provided by the CTRU to access the registration service. These codes will only be issued once a site has been fully approved and all the necessary documentation has been received at CTRU.

The following information will be required at registration:

- Participant details, including initials, sex and date of birth
- Site code for research site
- Confirmation of eligibility
- Confirmation of written informed consent and date
- Confirmation of completion of the baseline questionnaire (where applicable paper/telephone administration only)

- Whether the participant requires an electronic link to complete the baseline questionnaire and preferred method of receipt and contact details (email/text) (where applicable)
- Preferred method of follow up questionnaire administration (where applicable electronic/postal/verbal)
- Decision regarding optional consent to be contacted for WP3 including phone number and preferred method to receive further information

Once registration is complete, the system will allocate a participant ID number which will be shown on screen.

After registration the research site will:

- Add the unique participant ID number to the consent form if completed on paper
- Return a copy of completed paper consent forms, contact details form and paper baseline questionnaires (where applicable) to CTRU via secure file transfer
- Send the GP letter notifying the participant's GP of their participation in the study
- Arrange the CXR and LDCT appointments for the participant, including creation of new CXR/LDCT requests under the named responsibility of the local PI.
- Cancel the GP CXR request. Note: Responsibility for actioning test results will transfer to the local PI at this point

11.0 Treatment/Intervention Details

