12.2. Schedule of Events

Please see next page.

Study visit	Consent	Baseline	LDCT imaging appointment	CXR imaging appointment	HLH LDCT upload	HLH CXR upload	HLH LDCT report transfer	HLH CXR report transfer	Post-imaging clinical review of report	Follo	w up
Timeline	on or before day 0	Day 0	First test (LDCT) within 10 working days of GP CXR request, + additional 5 working days for CXR if unable to arrange on same day as LDCT		Within 2 working day of image acquisition		Within 2 working day of report being available ¹		Within 10 working days of report being available ²	4m post baseline +/- 2 weeks	12m post baseline +/- 2 weeks
Informed consent	Х										
Eligibility checks		Х									
Contact details form		Х									
EQ-5D questionnaire		X ³								X4	
Demographics, medical history, & baseline clinical assessments		X									
Registration in Gen24		Х									
Arrange CXR and LDCT appointments		Х									
Cancel GP CXR request		Х									
Send GP letter		Х									
LDCT ⁵			Х								
CXR ⁶				Х							
RUSAE reporting			Х	Х							
Send patient/GP non-attendance letter (where applicable)			Х	Х							
Manual transfer of scans to HLH record from local PACs OR check automatic transfer via HL7 has been successful					Х	Х					
Manual transfer of scan report from HLH into local record OR check automatic transfer to RIS has been successful							Х	Х			
Review reports & initiate standard care									х		
Send GP patient result letter									X		
Medical record review										Х	Х
eCRF completion		Х			Х	Х	Х	Х	Х	Х	Х

¹If the interval between HLH image upload and completion of reporting by HLH exceeds 5 working days please notify CTRU.

²If there is a delay between LDCT and CXR acquisition/report availability , the LDCT report should be reviewed first, followed by separate review of CXR report once available.

³administered by site in person/by telephone. If participant requires this to be sent electronically this will be administered by CTRU. Note: if electronic administration is required, contact details must be sent to CTRU on the day of the baseline visit.

⁴administered by CTRU if participant completing on paper/postal or electronic. Administered by site if participant requires telephone administration.

⁵Low-dose CT must be completed **prior** to chest X-ray.

⁶Patient should have both scans on the same day or within 5 working days of each other.

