12.3. Eligibility and Baseline Assessments

The following information will be collected at the baseline assessment:

- Data relating to the clinical assessment of eligibility
- Formal confirmation of eligibility

For participants that complete formal eligibility to proceed to registration the following baseline data will be recorded prior to registration:

- Demographic information
- Relevant medical history and clinical assessments
 - o BMI,
 - \circ index of multiple deprivation,
 - o ethnicity,
 - o mental health diagnoses,
 - smoking status and history,
 - symptom(s) prompting imaging and duration,
 - \circ Other parameters needed for lung cancer risk scores (PLCO_{M2012}/LLP_{v2}),
 - Name of General Practitioner who referred patient for chest X-ray and name of practice
- Questionnaire
 - health-related quality of life (EQ-5D-5L) in person/on paper/telephone/electronic administration (where applicable).

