16.1. Collection and analysis of economic data

16.1.1 Health-related quality of life

We will collect EQ-5D-5L at baseline and 4 months. Standard descriptive and graphical analyses will be conducted as per the EuroQol manual [42]. We will calculate utility values using the most appropriate value set, which could come from the second UK EQ-5D-5L valuation study or crosswalk to the EQ-5D-3L. If both of these are available for use then the base case analysis will be dictated by the NICE position statement. We will examine differences between measures at baseline and 4 months, stratified by lung cancer status, e.g., comparing EQ-5D-5L utility at the two timepoints using the paired t-test.

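### The electronic baseline EQ-5D-5L is sent after registration with no completion limit, contrary to Section 12.3, so some baseline forms can be answered after the LDCT and, less often, after its result

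*Protocol*

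**What the plan says.** The protocol gives two different rules for when the baseline EQ-5D-5L is completed.

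- **Section 12.3** says that "the following baseline data will be recorded prior to registration", and its list includes "health-related quality of life (EQ-5D-5L) in person/on paper/telephone/electronic administration (where applicable"). The electronic mode is named inside the pre-registration list.
- **Section 12.1** separates the modes. For paper and telephone: "Baseline questionnaires may be administered by the research team in person/on paper or over the telephone/on paper *prior* to registration". The electronic form instead "will be administered by the CTRU after registration. Non-responders to the electronic baseline questionnaire will receive 1 reminder".
- **Section 10.5** follows 12.1. One item required at registration is "Confirmation of completion of the baseline questionnaire (where applicable paper/telephone administration only"). For the electronic mode, registration records only "Whether the participant requires an electronic link to complete the baseline questionnaire" and how to send it.
- **Section 12.2** (schedule) puts the EQ-5D at Day 0. Footnote 3 adds that "if electronic administration is required, contact details must be sent to CTRU on the day of the baseline visit".

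On use, Section 16.1.1 plans to examine change from baseline to 4 months by lung cancer status, for example by "comparing EQ-5D-5L utility at the two timepoints using the paired t-test". Section 16.2 lists EQ-5D-5L utility among the MEDLEY data to go into the economic model.

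**The concern.** A baseline utility should describe the patient before the test. Under 12.1 an electronic form cannot satisfy 12.3, because the link goes out only after the event that 12.3 sets as the deadline. No section dates the reminder, gives a last acceptable completion date, or requires completion before the LDCT or before the result is communicated. The 4-month assessment, by contrast, has a window of plus or minus 2 weeks.

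A form answered once the patient knows the result already contains part of the effect of testing. In a comparison stratified by lung cancer status, the stratum most likely to be affected is also the smallest. Because paper and telephone forms precede registration, any contamination is confined to one mode of administration, so baseline would not mean the same thing across participants.

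**Working it through.** The protocol states no figure to reproduce on this point. The check adds up the protocol's own time limits and then sizes the possible effect under stated assumptions.

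**Step 1. Can an electronic form follow the scan?** Registration comes after the GP's request, and the LDCT is due no later than 10 working days after that request (Sections 12.2 and 12.4). The LDCT therefore falls 0 to 10 working days after registration. Section 10.3 allows same-day consent and notes that patients often attend within a day or two of seeing the GP, so short intervals are expected. The reminder date is not given. Over an assumed range:

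- reminder 5 working days after registration: after the LDCT for anyone scanned in the first week;
- reminder at 10 working days: at or after the LDCT for everyone scanned on schedule;
- reminder at 15 working days: see step 2.

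Completion after the scan is readily possible.

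**Step 2. Can it follow the result?** Inputs: upload up to 2 working days after acquisition (12.6); reporting about 5 working days (schedule footnote 1, a trigger for notification and not a cap); clinical review advised within 5 and at most 10 working days of the report (12.8); result letter copied to the patient (11.3).

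- Fast case, LDCT on the day of registration: 0 + 2 + 5 + 5 = working day 12, or sooner because each term can be shorter.
- Slow case, counted from the GP's request: 10 + 2 + 5 + 10 = about working day 27.

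A reminder at 15 working days would fall after the result in the fast case. Completion after the result is therefore possible, but it needs a participant who uses the electronic mode, does not answer the first link and responds late.

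**Step 3. How large could the effect be?** Expected cancers: 0.017 × 900 = 15.3, about 15 (Section 15.2). If *k* of *n* baseline forms are completed after the result and the result changes utility by *d*, the baseline mean shifts by (*k*/*n*) × *d*, and the mean change shifts by the same amount with the opposite sign. The protocol gives neither *k* nor *d*. Assuming *d* = 0.05 to 0.10 and *n* = 15:

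| Late forms, *k* | *d* = 0.05 | *d* = 0.10 |
|---|---|---|
| 1 | 0.003 | 0.007 |
| 2 | 0.007 | 0.013 |
| 3 | 0.010 | 0.020 |
| 6 | 0.020 | 0.040 |

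Shifts of 0.01 to 0.04 would need roughly 3 to 6 of the 15 forms (20% to 40%) to be completed after the result. Nothing in the protocol supports a share that high.

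**The case against.** The strongest reply is that this is one loose sentence. Sections 10.5, 12.1 and footnote 3 agree with each other and give sites a workable instruction; only 12.3 differs, and it carries a where-applicable qualifier. Administration by the site is the default, the electronic form is used only on request, and same-day transfer of contact details makes prompt dispatch likely. The paired t-test is offered only as an example, EQ-5D-5L carries no asterisk in Section 14.2, and the health economics analysis plan could deal with late forms.

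Much of this stands, and it limits the weight of the point. It does not remove it. The qualifier does not help, because the electronic mode is named within the pre-registration list. Footnote 3 governs dispatch and not completion. An analysis plan could discard late forms, but it could not recover a pre-test value that was never collected, nor reconcile 12.1 with 12.3.

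Three stronger readings are tempting, and the protocol does not support them:

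- **That the bias is material.** One or two late forms among about 15 cancers give at most 0.013 under the assumptions above, and the share of late forms is unknown.
- **That change is biased towards zero, in opposite directions for cancer and non-cancer groups.** This assumes that a non-cancer result reassures. Section 6.3 says that nodules and incidental findings on LDCT can cause anxiety, so both groups could shift the same way. Bias towards zero also needs the immediate effect to share the sign of the 4-month change, which is not established.
- **That any form completed after the scan is contaminated.** The mechanism is knowledge of the result; a form completed after the LDCT but before the result carries no result information.

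**Conclusion.** The contradiction between 12.3 and 12.1 is real, and so is the absence of a completion limit for the electronic form. As written, some electronic baseline forms can follow the scan and, less often, the result, while paper and telephone forms cannot. This can contaminate the stratified comparison in 16.1.1 and the utility data listed in 16.2, although 16.2 does not say which time point supplies the model.

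Size and direction cannot be derived from the protocol. The 0.003 to 0.013 illustration rests on an assumed effect of 0.05 to 0.10, one or two late forms, and about 15 cancers. Recruitment, diagnostic accuracy and prevalence are untouched, and EQ-5D-5L is not a progression outcome. This is an inexpensive improvement in data collection, best made before forms accrue.

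**What to change.** Reconcile Sections 10.5, 12.1, 12.2 (footnote 3) and 12.3 around one rule: the baseline EQ-5D-5L, in any mode, is completed after consent and before the LDCT. Then:

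- record the completion date for every mode, with a time stamp on electronic forms;
- if the electronic form is not in by the LDCT appointment, the site offers it on paper or by telephone before the scan;
- do not use as baseline any form completed after the result was communicated;
- flag and keep forms completed after the scan but before the result, with a sensitivity analysis that leaves them out. Discarding them outright would lose usable data from a stratum of about 15.

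The cost is protocol wording, a date field and a small added task for sites. The downside is slightly more missing baseline forms, which the fallback should limit.

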12.2. Schedule of Events

Please see next page.

Study visit	Consent	Baseline	LDCT imaging appointment	CXR imaging appointment	HLH LDCT upload	HLH CXR upload	HLH LDCT report transfer	HLH CXR report transfer	Post-imaging clinical review of report	Follo	w up
Timeline	on or before day 0	Day 0	First test (LDCT) within 10 working days of GP CXR request, + additional 5 working days for CXR if unable to arrange on same day as LDCT		Within 2 working day of image acquisition		Within 2 working day of report being available ¹		Within 10 working days of report being available ²	4m post baseline +/- 2 weeks	12m post baseline +/- 2 weeks
Informed consent	Х										
Eligibility checks		Х									
Contact details form		Х									
EQ-5D questionnaire		X ³								X4	
Demographics, medical history, & baseline clinical assessments		X									
Registration in Gen24		Х									
Arrange CXR and LDCT appointments		Х									
Cancel GP CXR request		Х									
Send GP letter		Х									
LDCT ⁵			Х								
CXR ⁶				Х							
RUSAE reporting			Х	Х							
Send patient/GP non-attendance letter (where applicable)			Х	Х							
Manual transfer of scans to HLH record from local PACs OR check automatic transfer via HL7 has been successful					Х	Х					
Manual transfer of scan report from HLH into local record OR check automatic transfer to RIS has been successful							Х	Х			
Review reports & initiate standard care									х		
Send GP patient result letter									X		
Medical record review										Х	Х
eCRF completion		Х			Х	Х	Х	Х	Х	Х	Х

¹If the interval between HLH image upload and completion of reporting by HLH exceeds 5 working days please notify CTRU.

²If there is a delay between LDCT and CXR acquisition/report availability , the LDCT report should be reviewed first, followed by separate review of CXR report once available.

³administered by site in person/by telephone. If participant requires this to be sent electronically this will be administered by CTRU. Note: if electronic administration is required, contact details must be sent to CTRU on the day of the baseline visit.

⁴administered by CTRU if participant completing on paper/postal or electronic. Administered by site if participant requires telephone administration.

⁵Low-dose CT must be completed **prior** to chest X-ray.

⁶Patient should have both scans on the same day or within 5 working days of each other.

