Participants	Adults aged 40 years and over with a GP referral for chest X-ray with symptoms of suspected lung cancer fulfilling NICE NG12 criteria									
Eligibility for WP1	Inclusion Criteria	Exclusion Criteria								
	 Must meet all the below: Age 40 years or more at the time the consent form is signed. Have had a CXR requested in general practice which fulfils NICE NG12 criteria (ref) Consent to participate in WP1 (written/verbal/eConsent). 	 Meet one or more of the below: Present with haemoptysis and/or have a pending urgent suspected cancer referral. Have had thoracic CT or LDCT within the last year Unable to, or chooses not to, receive a LDCT Currently undergoing anti-cancer treatment. Is pregnant* or currently breastfeeding. Previously registered in the MEDLEY study *Assessment of pregnancy potential (or exemption) completed as per national guidelines and/or local Trust policy. 								
Planned	900									
Sample Size										
Intervention	Each participant will receive both a chest x	-ray (CXR) and low-dose CT scan (LDCT)								
Follow up	12 months post registration									
schedule	Medical record review at 4 months and 12 months post registration									
	Objective	Outcome measure								
Primary (WP1)	Establish feasibility and deliverability of a diagnostic accuracy study.	 Recruitment rate Proportions of eligible patients consenting to participate Time from site approach to opening 								
	Estimate parameters for the design of a potential, future definitive trial.	Sensitivity and specificity of CXR vs LDCTEstimate of prevalence of lung cancer								
Value of Information analysis (WP2)	Undertake a model-based economic evaluation and a value of information analysis with respect to a definitive trial.	 Cost effectiveness of LDCT vs CXR Vol assessment for a definitive trial 								
Qualitative study (WP3)	Undertake an embedded qualitative study to obtain views on participation and non-participation, acceptability of trial design, recruitment and imaging requirements, and a stakeholder event to discuss implementation during and post-trial.	 Reasons for participating Barriers to participation Acceptability from patient perspective Acceptability from GP perspective Perspectives and priorities of key stakeholders 								

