6.3. The role for LDCT

Low-dose computed tomography (LDCT) produces more detailed images than CXR and exposes patients to less radiation than conventional CT. Although LDCT has been shown to be more accurate than CXR in asymptomatic patients [9] its accuracy compared to CXR in symptomatic patients is unknown [10]. LDCT scans take longer to acquire and interpret and are more expensive (£90 vs £27) than CXR [11]. LDCT is much more likely to lead to findings of incidental abnormalities, unrelated to patients' symptoms, or nodules which then require further tests and/or follow up, the majority of which are subsequently found to be benign [9, 12]. Such findings can lead to unnecessary anxiety and inconvenience for patients [13, 14]. The most robust comparison of LDCT and CXR is from a screening study in asymptomatic patients, undertaken in the US [9]. Sensitivities were determined with reference to cancers presenting within 12 months of each test. These were reported as 94% for LDCT (95% CI 91 to 96%) and 73% for CXR (95% CI 73 to 74). However, accounting for the additional cancers detected on LDCT which were probably present in the CXR arm at the time of screening but presented beyond the 12-month follow-up period, CXR sensitivity may be as low as 47% (136/284) even accounting for overdiagnosis [15]. A systematic review of CXR in symptomatic patients reported sensitivity between 77% and 80%, based on presentations of lung cancer within one year of the test [7]. This estimate will also be affected by cancers present at the time of the CXR but not presenting for several years [15]. As well as uncertainty about the difference in sensitivity between CT and CXR in symptomatic patients, there are no published data about the stage distribution of the cancers missed on CXR but that LDCT would detect (subsequently termed CT-extra cancers). Screening studies report increased proportions of early stage lung cancers detected by CT (70% stage I/II in NLST and 77% in NELSON) [9, 16]. However, the stage distribution of CT-extra cancers in symptomatic patients may be less favourable. Lung cancers that cause symptoms tend to be larger, and may be located in parts of the lung poorly evaluated on CXR (e.g. the central hilar regions). Tumour size and central location both predict earlier metastatic spread, so these symptomatic cancers that are

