8.1. WP1

WP1 aims to recruit 900 participants with symptoms that may suggest lung cancer who have been referred from primary care for CXR from at least five UK centres. Patients will be recruited from secondary care sites and will follow a standard care pathway. All patients will receive a LDCT as well as a CXR, and both LDCT and CXR will be reported by independent consultant radiologists. The LDCT will be used to guide clinical care by the secondary care team and the report will be sent to the referring GP. All participants will be followed up for a maximum of 52 weeks. Outcomes are defined in section 14 grouped as i) feasibility of deliverability; ii) qualitative acceptability; iii) estimates of diagnostic accuracy; iv) imaging logistics; v) clinical outcomes; vi) economic outcomes. Those outcome measures informing the decision criteria to progress to definitive trial are stated in sections 14.1 and 14.2. The reference standard will be cancer diagnosis within 12-months of clinical follow-

up, but cancer diagnoses resulting from the paired LDCT (i.e. MDT approved diagnosis within 3 months of LDCT) will also be reported as a contemporaneous reference standard.

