12.4. WP1 Registration

Registration will be completed at the baseline visit prior to booking the imaging appointments by a member of the research team after consent using the CTRU 24 hour system.

Following registration, the LDCT and CXR appointments will be arranged. Note: the LDCT must be completed before the CXR and within 10 working days of the GP CXR request, and there will be a maximum of 5 working days between the imaging tests.

The following information will be recorded **after** registration:

- Participant ID number
- Date of LDCT appointment
- Date of CXR appointment

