12.9. WP1&2 Follow Up Assessments

All participants will be followed up for a maximum of 52 weeks.

Month 4 Record Review and Questionnaire

A member of the research team will review the participant's medical records and record the following (relating to clinical activity resulting from MEDLEY imaging findings):

- Investigations
- Diagnoses (lung cancer (including stage), indeterminate nodules, and incidental findings) and date
- Treatments
- Possible harms

Participants will also complete an EQ-5D-5L via their preferred method of administration.

Month 12 Record Review

A member of the research team will review the participant's medical records and record the following:

- Investigations
- Diagnoses (lung cancer (including stage), indeterminate nodules and incidental) and date
- Treatments
- Possible harms

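### The month-12 record review may be done up to 2 weeks early, so a compliant review can close the 12-month reference standard before the year is complete

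*Protocol*

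**What the plan says.** Section 8.1 states: "The reference standard will be cancer diagnosis within 12-months of clinical" follow-up. Section 14.1.2 gives the period as one year. Section 15.1 takes per-protocol cancer status at the end of the 12-month follow-up, and section 15.1.6 bases prevalence on diagnoses confirmed after 12 months.

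The assessment that supplies these data is the second of two record reviews (section 12.9). The Schedule of Events in 12.2 times it at "12m post baseline +/- 2 weeks", and nothing is scheduled after it. Sections 8.1 and 12.9 also cap follow-up: "All participants will be followed up for a maximum of 52 weeks".

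The clock runs from registration. The Study Summary (4.0) has "Medical record review at 4 months and 12 months post registration", and section 12.4 says "Registration will be completed at the baseline visit prior to booking the imaging appointments". The tests therefore come on or after day 0. Section 12.2 allows "First test (LDCT) within 10 working days of GP CXR request", plus an "additional 5 working days for CXR if unable to arrange on same day as LDCT".

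Section 6.3 describes the main external benchmark, a screening study, on a different clock: "Sensitivities were determined with reference to cancers presenting within 12 months of each test".

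**The concern.** A retrospective record review has no evident need for an early side to its window. If the notes are opened before the year is up, any cancer diagnosed afterwards is never recorded, and the participant is classed as cancer-free. Recorded diagnosis dates let an analyst cut off a late review at one year. They cannot recover what an early review did not see, so the analysis plan cannot repair this. The window is fixed in the protocol.

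The error has a direction. LDCT guides care (sections 8.1 and 11.3), so cancers it detects should be diagnosed early. Those still undiagnosed after eleven months are mainly those LDCT missed or left indeterminate. Losing one removes it from the sensitivity denominator and from the prevalence numerator. The length of follow-up also comes to depend on the day a site happens to open the notes.

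**Working it through.** The protocol gives no figure of its own for this point, so there is none to reproduce.

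**Inputs**
- Review window: 365 − 14 = day 351 to 365 + 14 = day 379 from registration (12.2).
- LDCT limit: 10 working days after the GP request = 14 calendar days. CXR limit: 5 working days more = 7 calendar days (12.2, 12.4). Public holidays are ignored.
- Expected cancers: 1.7% × 900 = 15.3 (15.2).
- LDCT sensitivity: 90% (the illustration in 15.2) to 94% (the screening study in 6.3).

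**Step 1: the protocol's own clock.** A review on day 351 falls 365 − 351 = 14 days short of 12 months. This needs no assumption.

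**Step 2: time after the tests.** Days observed = 365 + window offset − day of test. Each cell gives LDCT / CXR, with CXR at its limit after LDCT.

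| GP request and imaging | Review at −14 days | On time | +14 days |
|---|---|---|---|
| Request on registration day; LDCT day 14, CXR day 21 | 337 / 330 | 351 / 344 | 365 / 358 |
| Request 5 working days before registration; LDCT day 7, CXR day 14 | 344 / 337 | 358 / 351 | 372 / 365 |
| LDCT day 0, CXR day 7 | 351 / 344 | 365 / 358 | 379 / 372 |

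The extreme is 365 − 337 = 28 days short for LDCT and 365 − 330 = 35 days short for CXR. Of this, 14 days come from the window and the remaining 14 or 21 from counting from registration.

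**Step 3: expected loss.** Lost false negatives = 15.3 × (1 − sensitivity) × days short / 365, assuming they surface evenly over the year.
- LDCT false negatives: 15.3 × 0.06 = 0.92 to 15.3 × 0.10 = 1.53.
- 14 days short for everyone: 0.92 × 14/365 = 0.04 to 1.53 × 14/365 = 0.06.
- 28 days short for everyone: 0.92 × 28/365 = 0.07 to 1.53 × 28/365 = 0.12. Apparent LDCT sensitivity goes from 94% to 94.4%, or from 90% to 90.7%.
- If instead all of them surface after month 4, over the remaining 52 − 17 = 35 weeks: 0.92 × 4/35 = 0.10 to 1.53 × 4/35 = 0.17.
- Prevalence: 0.12/900 = 0.013 percentage points.

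The same formula for CXR (73% to 80% sensitivity, 35 days) gives 0.29 to 0.40 lost. That is an upper bound: it lets CXR misses surface evenly over the year, whereas LDCT should bring most of them to diagnosis early. Cancers that LDCT left indeterminate are not in the calculation, because the protocol gives no number for them.

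**The case against.** The strongest reply is that the registration clock is a deliberate and consistent choice. Sections 4.0 and 12.2 both use it, and the reference standard is tied to clinical follow-up. A reader might infer from section 6.3 that a year from each test is owed. That sentence describes an external study, and objective 7.2b asks only whether the estimates are consistent with published ones. This stands: the protocol does not promise a from-test year, and the firm shortfall is 14 days.

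A reader might also take 4 to 5 weeks as the usual shortfall. It requires registration on the day of the GP request, both tests at their limits and the earliest permitted review, all together. Section 10.3 expects imaging to be prompt. This stands too.

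The +2 week side might be read as admitting diagnoses made after one year. It need not: a review opened in week 54 can abstract 52 weeks of data, and diagnosis dates are recorded. The 52-week wording is merely unclear about which of the two it limits.

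Finally, both contemporaneous comparisons, the starred accuracy outcome in 14.1.2 and the 3-month standard in 8.1, escape the problem. The 12-month comparative accuracy outcome is unstarred, and section 15.2 disclaims any pre-specified precision.

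None of this answers the early side. A review before day 365 is incomplete on the protocol's own terms, and nothing later completes it.

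**Conclusion.** The point holds as a small, definite flaw in the data-collection window. It affects the 12-month sensitivity and specificity, and the starred prevalence outcome (14.1.4), by a fraction of one cancer. The 14-day shortfall is certain for any review done on the first permitted day. The 28- and 35-day figures are extremes. The expected loss rests on 1.7% prevalence, 90% to 94% LDCT sensitivity and evenly spread late diagnoses. It stays well under one cancer if the last assumption is changed as shown.

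A reader might infer a larger effect from the leverage of a single case: with 15 cancers, losing one false negative turns 14/15 (93%) into 14/14 (100%). The arithmetic is right, but an expected loss of about 0.1 makes that an unlikely event and not the size of the bias. The reason to act is that the bias has a known direction, cannot be undone at analysis and is cheap to remove.

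**What to change.** - In 12.2 and 12.9, let the month-12 review open no earlier than a full 12 months, for example 0 to +4 weeks. Preferably count from the later of the two imaging dates, or from registration if no imaging was done.
- In 8.1, 14.1.2 and 15.1, count as reference-positive only diagnoses dated within 365 days of one stated start date per participant, for example the LDCT date, or registration if no LDCT was done. One start date keeps a single reference status for both tests and covers registered participants without imaging.
- In 8.1 and 12.9, reword the 52-week maximum as the period of data abstracted, not the date of the review, and match it to the same start date.
- Reconcile the maximum interval between the tests, which is 7 working days in 10.3 but 5 in 12.2, 12.4 and 15.1, since it sets the later imaging date.

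Cost: protocol wording and a later finish. The last permitted review moves from day 379 to 365 + 28 = day 393 if counted from registration (14 days, about 2 weeks). Counted from a CXR on day 21, it moves to 21 + 365 + 28 = day 414 (35 days, about 5 weeks). Database lock moves with it. No visit or procedure is added.
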